6.2 Visits schedule

(ICH E3; 9.5.1. ICH E9; 2.2.2)

The following table presents the relation between visits and medical assessments planned for this study:

SAP Table. 1 Visits schedule

Assessment	Screening	Baseline	Treatment period: 2 -weeks post-baseline evaluation	Treatment period: Complete evaluations	Treatment period: Routine evaluations	End of treatment visit: After progression or at the end of treatment for any other reason	Follow-up
	(2-4 weeks as maximum before baseline)	Day 0 (pre-treatment)	After 2 weeks	After 12, 24, 36, 48, 60, 72 weeks from first dose	After 6, 18, 30, 42, 54, 66, 78 weeks from first dose	Within 4 weeks after end of treatment (only if end of treatment is not confirmed in some of the scheduled full visits)	After progression or end of treatment for any other reason, after 12,24,36,48, 60, 72, 78 weeks after first dose
Written Informed Consent	X						
Sample (tissue) to the central lab	X [1]					X (if available)	
Medical History		X		X			
Physical examination, ECOG Performance Status, Vital Signs, body weight		X [2]		X [2]	X [2]	X [2]	
Recording of symptoms		X		X	X	X	
Pregnancy Test		X [3]					
Hematology		X [4]		X [4]	X [4]	X [4]	
Renal function		X [4]		X [4]	X [4]	X [4]	
Blood Chemistry		X [4]		X [4]	X [4]	X [4]	
Coagulation		X [4]		X [4]	X [4]	X [4]	
Urine dipstick test for analysis of proteinuria		X [4]		X [4]	X [4]	X [4]	
ECG		X [5]		X	X (only if clinically required)	X	
Tumor Assessment		X [6]		X [6]		X [6]	

Serum/plasma sample for translational research		X	X	X		X	
Antineoplastic therapy		X	X	X	X	X	X
Concomitant Medication	X		X [7]	X [7]	X [7]	X [7]	
Adverse Events			X	X	X	X	X [8]
Survival			X	X	X	X	X

1. EGFR results from test performed locally in the same laboratory than the central one up to 28 days before inclusion will be accepted.
2. Vital signs include pulse and temperature.
3. A negative serum or urine pregnancy test up to 7 days before inclusion will be accepted.
4. Hematology, renal function, blood chemistry and coagulation tests performed up to 72 hours before inclusion and before the corresponding date of each visit will be accepted.
5. ECG performed up to 14 days before inclusion and before the corresponding date of each visit will be accepted.
6. Assessment procedures should be the same at every visit. Baseline tumor assessments should include, at least, chest and abdominal CT. If, in the opinion of the investigator it is clinically indicated, other radiological evaluations may be performed (PET-CT, MRI). PET-CT, MRI performed up to 28 days before inclusion and up to 14 days before every visit during treatment period including end of treatment visit will be accepted
7. Every concomitant medication will be recorded, including analgesics.
8. Every new AE identified up to 28 days after administration of last dose of study treatment or until a maximum of 78 weeks after first dose should be recorded on the corresponding CRF page (AE).

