- Until the end of study, after a maximum of 78 weeks from the administration of the first dose of treatment by the last enrolled patient (see Section 3.7).
- Study is canceled by the sponsor.

In the event a dose change is required during the treatment, 40 mg tablets can be administered as described in section 6.9.

Treatment with osimertinib (AZD9291) is continuous, and every 21-day period will be considered one cycle. The treatment will begin on day 1 of the first cycle.

Follow-up visits will take place every 6 weeks to obtain basic safety data and every 12 weeks to obtain complete efficacy and safety data.

At the end of the study, patients may continue taking commercial osimertinib (TAGRISSO™) if it provides benefits in the investigator's opinion.

Follow-up phase:

Once the treatment phase is completed, a biopsy should be performed to identify acquired mechanisms of resistance to the drug and the follow-up phase will begin. The frequency of clinical assessments during this phase of the study will not differ from that performed in the course of standard clinical practice. Follow-up visits will take place every 12 weeks; information on the patient's health state will be included in the CRF, as well as any treatment received until the end of study.

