ECOG performance status: Performance status will be determined using the ECOG performance status scale. Wherever possible, the patient's performance status should always be assessed by the same personnel throughout the study.

Grade	Scale
0	Fully active, able to carry on all pre-disease performance without restriction.
2	Ambulatory and capable of all self-care but unable to carry out any work activities. Up and about more than 50 % of waking hours.
4	Completely disabled. Cannot carry on any self-care. Totally confined to bed or chair.

Adverse events and toxicity to treatment: Safety and tolerability of all patients will be closely monitored throughout study treatment and the follow-up period. Patients will be assessed in order to detect any side effects before administering new bottles of the study treatment. New bottles of treatment will only be administered if clinical evaluation and local laboratory test results are acceptable.

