The initial dose of 80 mg AZD9291 can be reduced to 40 mg AZD9291 once daily, under circumstances described in Section 6.9. Doses should be taken approximately 24 hours apart at the same time point each day. If a subject misses a scheduled dose, it is acceptable to take the dose within a window of 12 hours. If it is more than 12 hours after the dose time, the missed dose should not be taken, and subjects should be instructed to take the next dose at the next scheduled time. If a subject vomits after taking their osimertinib (AZD9291), they should not make up for this dose, but should take the next scheduled dose. Any change from dosing schedule, dose interruptions, and dose reductions should be recorded in the CRF.

Drug treatment is to begin within 2-4 weeks of reception of the tumor sample at the central reference laboratory. Patients will continue receiving the assigned therapy until objective disease progression, symptomatic deterioration, occurrence of an unacceptable side effect, death, withdrawal of consent or the end of the trial (78 weeks from the first dose of the last enrolled patient), whichever occurs first.

However, patients may continue to receive treatment with commercial osimertinib (TAGRISSO) according to the investigator's judgment. In this case, the investigator should follow-up on the patient in an appropriate manner, according to standard clinical practice.

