6. STUDY DESIGN

6.1 General study design and plan

(ICH E3;9.)

Identify the study design, including the following:

- This is a multicenter, open-label, single-arm non-controlled phase IIa trial. The design of this study is divided into three well-defined phases:
 - **Screening phase**

During this phase, subject eligibility is determined, including the genotyping of the tumor and documentation of baseline characteristics.

[figure not shown]
- **Treatment phase:**

When a patient carrying both mutations is identified and the study screening criteria have been met, the patient will receive a dose of osimertinib (AZD9291) 80 mg every 24 hours, in tablets for oral administration. The study treatment will continue until one of the following situations arises:

- Disease progression is confirmed radiologically and unequivocally, except for new metastases in CNS or isolated progression of previously-treated lesions in the CNS.
- Adverse event(s) which, according to the protocol or in the opinion of the investigator, can cause serious or permanent damage or which rule out further treatment with the study drug.
- General or specific changes in the patient's health state which, in the opinion of the investigator make further treatment unacceptable.
- Major study protocol non-compliance.
- Patient's withdrawal from the study.
- Dead.
- After a maximum of 78 weeks from the patient first study treatment dose intake.
- Study is canceled by the Sponsor.

- **Follow-up phase:**

Once the treatment phase is completed, a biopsy should be performed to identify acquired mechanisms of resistance to the drug and the follow-up phase will begin.

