6.6 Interim analysis

An interim analysis will be performed when 21 patients have been assessed up to 42 weeks or withdrawn from the study. The interim analysis will assess the primary endpoint and all the secondary safety and efficacy objectives limited to a window of up to 42 weeks. The first interim report will only include the summary of study accrual, the clinical and demographic summary, the primary efficacy analysis and the report of toxicity. This first report has developed to not delaying the go/not go decision in the first stage. The other results will be presented later. After the database

lock at 42 weeks, these patients will continue to be treated and monitored until progression, death or treatment discontinuation. The decision to stop and continue the trial should be agreed by the steering committee after reviewing the interim safety and efficacy data.

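### The protocol and SAP run the 78-week limit from different starting points, and the SAP's adverse-event schedule and footnote follow the shorter one, so late safety data may be incomplete

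*SAP*

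**What the plan says.** **Limits counted from each patient's own first dose (SAP).**
- SAP 6.1, General study design and plan, lists among the reasons for ending treatment: "After a maximum of 78 weeks from the patient first study treatment dose intake".
- SAP 6.2, Table 1, sets the routine on-treatment visits at "After 6, 18, 30, 42, 54, 66, 78 weeks from first dose". The complete evaluations end at week 72 and the follow-up column at week 78, all from first dose.
- Note 8 to that table sets the period for recording new AEs: "up to 28 days after administration of last dose of study treatment or until a maximum of 78 weeks after first dose". The second limb, "until a maximum of 78 weeks after first dose should be recorded", is the one that counts from first dose. In the Adverse Events row the note is attached only to the Follow-up cell; the on-treatment and end-of-treatment cells carry no note.

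**Limits counted otherwise.**
- Protocol 3.2 lets treatment run until the end of study, "after a maximum of 78 weeks from the administration of the first dose of treatment by the last enrolled patient". Protocol 6.5 uses the same clock.
- SAP 6.6 says that after the interim database lock "these patients will continue to be treated and monitored until progression, death or treatment discontinuation". It mentions no 78-week limit.

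**Safety collection in the protocol.** Protocol 5.2 lists AE assessment at each 6-weekly and 12-weekly visit and adds: "Safety and tolerability of all patients will be closely monitored throughout study treatment and the follow-up period". It gives no per-patient stop at week 78.

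**The concern.** The two documents use the same number of weeks with different starting points. Under the protocol, and under SAP 6.6, anyone enrolled before the last patient may still be taking study drug after their own week 78. The SAP table has no numbered visit after that week, and its only statement on how long AEs are recorded contains a 78-week maximum.

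Safety and tolerability are a stated secondary objective. The treatment period runs to the last dose (Protocol 3.5), and the safety analysis begins with exposure, including its duration (Protocol 8.3, SAP 7.3). If sites or the CRF followed the SAP table, exposure could be counted over time in which events were not systematically collected, and late-onset toxicity would be described incompletely.

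There is a second problem that does not depend on the protocol. If the maximum in note 8 overrides the 28-day limb, patients whose last dose falls near week 78 lose part or all of the post-dose window that the same note provides.

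**Working it through.** The plan gives no figure of its own on this point, so there is nothing to reproduce. The check is calendar arithmetic.

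**Inputs**
- Protocol treatment limit: 78 weeks after the last enrolled patient's first dose (Protocol 3.2, 6.5).
- SAP treatment limit and last numbered visit: week 78 from own first dose (SAP 6.1, Table 1).
- Post-dose AE window: 28 days, that is 4 weeks (note 8).
- G: weeks from a given patient's first dose to the last enrolled patient's first dose. The documents do not give it. The values 26 and 52 are assumptions. The upper value, about 104 weeks, is the 24-month recruitment period in the SAP section headed Final analysis.

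**Step 1. Time on drug past week 78 under the protocol clock**

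Maximum time on drug = 78 + G. Share after week 78 = G / (78 + G). AE window past week 78, with the 28-day tail = G + 4.

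| G (weeks) | Maximum on drug (weeks) | Share after week 78 | AE window past week 78 (weeks) |
|---|---|---|---|
| 0 | 78 | 0% | 4 |
| 26 | 104 | 26/104 = 25% | 30 |
| 52 | 130 | 52/130 = 40% | 56 |
| 104 | 182 | 104/182 = 57% | 108 |

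These are maxima for a patient who stays on drug to the end of study, not averages over the trial.

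**Step 2. The 28-day window if the 78-week maximum governs**

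For a last dose at week L, days kept = min(28, 7 × (78 − L)), and none once L reaches 78.
- L = 74: 7 × 4 = 28 days, so the window is intact.
- L = 76: 7 × 2 = 14 days.
- L = 78: 7 × 0 = 0 days.

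The cut starts with any last dose after week 74. It applies even if SAP 6.1 stands and nobody is treated beyond week 78.

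**Step 3. Which Table 1 cells could capture AEs after week 78**
- The numbered on-treatment visits end at week 78 and the follow-up visits at week 78. Neither column covers later treatment.
- The end-of-treatment visit is tied to stopping (within 4 weeks), not to a week number, and has an AE cell. It could fall after week 78. It is a single visit, required only when the end of treatment is not confirmed at a scheduled full visit, so it does not replace visits during continuing treatment.
- Note 8 is attached to the Follow-up cell only. The on-treatment gap therefore comes from the visit columns; the note's own effect is on the post-treatment window.

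**The case against.** The strongest case on the other side has four parts.

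**The SAP is consistent with itself.** SAP 6.1 ends treatment at each patient's week 78, so a schedule ending there covers all treatment. This stands only if SAP 6.1 is the operative rule. It conflicts with Protocol 3.2 and 6.5, and SAP 6.6 continues stage 1 patients without that limit. The truncated 28-day window in step 2 remains even under SAP 6.1.

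**Note 8 is not a clear cap.** Its two limbs are joined by *or*, with no statement of which prevails. Under the 28-day limb nothing is cut. This is correct, and it is why the note needs rewording: the mention of a maximum invites the restrictive reading.

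**The protocol already covers collection.** AEs are assessed at every treatment visit, and SAP 7.3 does not truncate the safety analysis at week 78. This also stands. A reader might infer that the SAP causes on-treatment toxicity after week 78 to be lost; the documents do not show that. The protocol text available for review contains no AE-reporting section, so its formal reporting period could not be compared.

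**No planned rate would be biased.** A reader might infer that AE rates per unit of exposure are understated. Neither Protocol 8.3 nor SAP 7.3 plans such a rate; exposure is described and AEs are tabulated.

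A reader might also try to estimate the share of all exposure falling after week 78. With exponential time on drug, assumed medians of 12 to 24 months and uniform accrual over 24 months, that share is 20–29%. With accrual over 26 or 52 weeks it is 8–11% or 13–19%, and under SAP 6.1 it is zero. The medians are in neither document, and SAP section 9 reports that the trial was closed to further accrual after the interim analysis, so the planned 24 months cannot be assumed. None of these percentages can be stated as the size of the problem.

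**Conclusion.** The concern holds as a conflict between the documents with a risk to late safety data.

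- The 78-week clocks differ: last enrolled patient's first dose in Protocol 3.2 and 6.5, own first dose in SAP 6.1, Table 1 and note 8, and no stated limit for stage 1 patients in SAP 6.6.
- Under the protocol clock a patient may be on drug for up to 78 + G weeks, with a share G/(78 + G) of that maximum beyond the SAP's numbered visits: 25% at G = 26 and 40% at G = 52. G is not given, and early closure of accrual probably makes it smaller than the recruitment plan implied.
- If the maximum in note 8 governs, the 28-day window is shortened for any last dose after week 74. This depends on how the note is read, but not on G or on which treatment limit applies.

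The documents support calling this a risk of incomplete late safety data if sites or the CRF follow the SAP table. They do not show that events went unrecorded or that any planned safety estimate is biased.

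**What to change.** 1. Reconcile SAP 6.1 (General study design and plan), SAP Table 1, note 8 and SAP 6.6 with Protocol 3.2 and 6.5, so that one starting point for the 78 weeks applies throughout. Which treatment duration is right is for the sponsor to settle, not this review.
2. Whichever duration is kept, reword note 8 so that new AEs are recorded until 28 days after the last dose of study drug, with no separate limit counted from first dose.
3. Extend the AE visits in Table 1 to cover all on-treatment time, for example by continuing the existing 6-weekly pattern until treatment ends instead of listing week numbers up to 78.

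The cost is a change to one footnote and some column headings, plus slightly more data entry. Under the protocol, patients on treatment are already seen every 6 weeks with AE assessment, so no on-treatment visits are added.

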6.3 Study population

(ICH E3;9.3. ICH E9;2.2.1)

Patients diagnosed with stage IIIB or IV non-small cell lung cancer carrying the EGFR activating mutation and confirming concomitant T790M mutation during screening who have not received prior treatment for this advanced disease will be enrolled in this study. Patients are not eligible if they are candidates for local curative treatment.

The analysis of EGFR mutational status (del19, L858R, L861Q or G719X) may be previously performed at each of the participating sites, but the tumor material taken from all patients should be submitted to the central laboratory for supportive analysis and T790M mutation analysis.

The patient's signed informed consent should be obtained before sending the tumor tissue sample to the central laboratory.

6.3.1 Inclusion criteria

Patient eligibility will be reviewed and documented by a suitable member of the investigator's study team before the patients are enrolled in the study.

Patients must meet all the following inclusion criteria to be enrolled in the study:

1. Patient aged 18 years or older.
2. Patients with histological confirmation of locally advanced or metastatic, non-squamous non-small cell lung cancer (NSCLC) with an activating EGFR mutation and concomitant T790M mutation who are not candidates for local curative treatment.
3. Patients with a M1a stage according to the TNM version 7 including M1a (malignant effusion) or M1b (distant metastasis), or locally advanced disease that is not a candidate for curative treatment (including patients who progress after chemoradiotherapy in stage III disease).
4. Patients with a EGFR deletion or mutation in exon 19, exon 21 (L858R, L861Q) or exon 18 (G719X) and concomitant T790M mutation before treatment confirmed centrally.
5. ECOG (*Eastern Cooperative Oncology Group*) performance status less than or equal to 2.
6. Existence of measurable or evaluable disease (as per RECIST 1.1 criteria). Patients with asymptomatic and stable brain metastases are eligible for the study.
7. Possibility of obtaining sufficient tissue sample, via a biopsy or surgical resection of the primary tumor or metastatic tumor tissue, within the 60 days prior to study entry.
8. Life expectancy \geq 12 weeks.
9. Adequate hematologic function: Absolute neutrophil count (ANC) $> 1.5 \times 10^9/L$, platelet count $> 100.0 \times 10^9/L$ and hemoglobin $> 9.0 \text{ g/dL} (> 6.2 \text{ mmol/L})$.
10. Adequate coagulation: INR ≤ 1.5 .
11. Adequate liver function: Total bilirubin $< 1.5 \times \text{ULN}$, ALT and/or AST $< 2.5 \times \text{ULN}$, alkaline phosphatase $< 5 \text{ ULN}$, except in the presence of single bone metastases and in absence of any liver disorders.

12. Adequate renal function: Calculated creatinine clearance > 50 mL/min (Cockcroft-Gault) and proteinuria < 2+ (dipstick).
13. Capacity to swallow, patient capable of completing treatment and accessible, ensuring proper follow-up.
14. Patients able to complete study and within geographical proximity allowing for adequate follow-up.
15. Resolution of all acute toxic effects of previous anti-cancer therapy (which can only be adjuvant or neoadjuvant) or surgical interventions not exceeding grade ≤ 1 according to the NCI CTCAE version 4.0 (except for alopecia or other side effects that the investigator does not consider to be a risk to patient safety).
16. All men or women of childbearing potential must use a contraception method during the study treatment and for at least 12 months after the last dose of the study drug. Sexually active men and women of childbearing potential who are unwilling to use a contraception method are not eligible for the study.
17. The written informed consent (IC) must be signed and dated by the patient and the investigator before any study intervention takes place.

6.3.2 Exclusion criteria

Any patient meeting **ANY** of the following criteria will be excluded from the study:

1. Locally advanced lung cancer candidate for curative treatment through radical surgery and/or radio(chemo)therapy.
2. Patients diagnosed with another lung cancer subtype, patients with mixed NSCLC with predominantly squamous cell cancer, or with any small-cell lung cancer component.
3. Patients with a EGFR deletion or mutation in exon 19, exon 21 (L858R, L861Q) or exon 18 (G719X) and concomitant T790M mutation before treatment that have not been confirmed centrally.
4. Patients who have received prior antineoplastic treatment for advanced disease.
5. Second active neoplasia; e.g. patients diagnosed with a potentially lethal cancer for which they may be receiving treatment (but are not obliged to do so).
6. Patients with just one measurable or evaluable tumor lesion that has been resected or irradiated prior to their enrollment in the study.
7. Medical history of Interstitial Lung Disease (ILD) induced by drugs, radiation pneumonitis requiring steroid treatment or any evidence of clinically active ILD.
8. Any of the following criteria:
 - Corrected QT Interval (QTc) >470 msec, obtained from 3 ECGs at rest, using the QTc value determined according to the clinical screening ECG machine.
 - Any clinically significant abnormality in ECG rhythm, conduction or morphology at rest.

- Any factor that increases the risk of QTc prolongation or risk of irregular heartbeat or sudden inexplicable death under the age of 40 in first-degree relatives or any concomitant medications that prolong the QT interval.

9. Uncontrolled, active or symptomatic metastases of CNS, carcinomatous meningitis or leptomeningeal disease indicated by known clinical symptoms, cerebral edema and/or progressive neoplasia. Patients with history of CNS metastasis or compression of the spinal cord are eligible if they have received local final treatment (e.g., radiotherapy, stereotactic surgery) and if they have remained clinically stable without using anticonvulsants and corticosteroids for a minimum of 4 weeks prior to the first day of study treatment.
10. Refractory nausea and vomiting, chronic gastrointestinal disease, inability to swallow study drug or significant intestinal resection that restricts the adequate absorption of osimertinib (AZD9291).
11. Patients who have had a surgical procedure unrelated to the study within 7 days prior to the administration of the drug or a significant traumatic lesion during the 4 weeks prior to starting the administration of the study drug, patients who have not recovered from the side effects of any major surgery or patients who might need major surgery during the course of the study.
12. Pregnant or breastfeeding women. Women of childbearing potential, including women who had their last menstrual period within the last two years, must have a negative serum or urine pregnancy test in the 7 days prior to the start of the treatment.
13. Patients who are not willing to use an adequate contraception method until 12 months after the last dose of study treatment.
14. Patients with a serious concomitant systemic disorder (e.g., active infection, including HIV or heart disease) that is incompatible with the study (in the opinion of the investigator), history of bleeding diathesis or anticoagulant therapy (the use of low molecular weight heparin is permitted provided that it is used for prophylaxis).
15. Inability to swallow tablets.
16. Patients with a history of cancer that has been completely treated, with no evidence of malignant disease currently cannot be enrolled in the study if their chemotherapy was completed less than 6 months prior and/or have received a bone marrow transplant less than 2 years before the first day of study treatment.
17. Prior treatment with cytotoxic chemotherapy for advanced NSCLC; neoadjuvant/adjuvant chemotherapy is permitted if at least 6 months have elapsed between the end of chemotherapy and the first day of study treatment.
18. Patients who have received prior EGFR treatments for lung cancer.
19. Patients who have received treatment with an investigational drug within 3 weeks before the first day of study treatment.
20. Treatment with prohibited drugs within 14 days before the first day of study treatment.
21. Any other reason that the investigator deems to be incompatible with the patient's participation in the study.

